Baseline characteristics of patients who received IV rt-PA and who didn't receive reperfusion treatments will be described, both before and after PSM. The absolute standardised difference (ASD) between the PS-matched cohorts will be calculated, where an ASD of at least 10% ASD will be considered a meaningful difference.

In the primary analysis, all patients who received endovascular treatment will be excluded. For the primary outcome, all-cause mortality at 1-year (mRS=6), will be evaluated using from the Kaplan-Meier curve. The percentage of 1-year mortality with 95% CIs in the 2 PS-matched cohorts will be calculated separately. Cox regression models will be used to estimate the hazard ratio for the primary outcome between PS-matched cohorts.

For the secondary outcomes, descriptive summaries will be conducted in the PS-matched cohorts separately. For categorical variables including functional independence (mRS 0-2), favourable clinical outcome (mRS 0-1) and outcome of mRS 5-6, the percentage and 95% CI will be calculated. A logistic regression model will be used to calculate odds ratios for functional independence (mRS 0-2), favourable clinical outcome (mRS 0-1) and outcome of mRS 5-6. For the distribution of mRS at 1 year, an ordinal logistic regression model will be used to calculate the odds ratio and 95% CI.

The primary and secondary outcomes will be analysed using the same method described above in following subgroups:

- Baseline NIHSS score (0-4, 5-10, 11-15, 16-21 and \geq 22)
- Onset to treatment time (\leq 90 mins, 91-180 mins, and 181-270 mins)
- Age (18-80 years, $>$ 80 years)
- rt-PA dose (low dose of \sim 0.6 mg/kg, standard dose 0.9 mg/kg)

Subgroup analyses will be conducted only when the patient number of each subgroup is equal to or exceeds 6069 or 5400 based on 2:1 or 1:1 treatment ratio assumption, respectively.

iii. Safety analysis

This study is a NIS based on existing data. From safety information collecting and reporting perspective, this study will not involve individual medical record review, thus no adverse event/adverse drug reaction information is required to collect. The analysis refers to [Section ii.](#)

H) QUALITY CONTROL

The study will strictly follow BI standard operation procedures (SOPs). In addition, this study will follow key elements of the Guideline for GPP. The statistical analytic approach will be reviewed/repeated by a second analyst. The study report will be reviewed, approved and archived per BI SOP.

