All the data cleaning, integration, analysis will be conducted under the guidance and supervision of ZSQCC.

Greater details are documented in the NIS-DMRP.

I) LIMITATIONS OF THE RESEARCH METHODS

This is a NIS based on existing data, although PSM is used, we cannot rule out the influence of other unmeasured confounding factors. In this study, potential limitations of the study design can be listed as:

- Zhejiang is an economically advanced province in China. In this study, AIS patients who received treatment or arrived or were admitted to the hospital within 4.5 hours of symptom onset in this study will be analysed and may not be fully representative to all AIS patients in China.
- AIS patient data from the ZSQCC platform were reported by the stroke centres without external monitoring.

- The treatment adapted for AIS patients may be different among stroke centres.
- The completeness of the captured data and potential for misclassification of data could differ among stroke centres.
- Some important variables may not be collected in the database. For example, patients' education level was not available in the database.

J) OTHER ASPECTS**i. Data quality assurance**

A quality assurance audit/inspection of this study may be conducted by the investigator or by IRBs / Independent Ethics Committee (IECs) or by regulatory authorities. The quality assurance auditor will have access to the investigator's study-related files and correspondence of this study.

ii. Study records**1. Source documents**

Source documents provide evidence for the existence of the patient and substantiate the integrity of the data extracted.

2. Direct access to source data and documents

The investigator/institution will permit study-related audits, IRB/IEC review and regulatory inspection, providing direct access to all related database/documents. All source documents, including progress notes must be available at all times for review by the inspection by health authorities.

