9.3 Is a coding system described for:				
9.3.1 Exposure? (e.g. WHO Drug Dictionary, Anatomical Therapeutic Chemical (ATC) Classification System)				NA
9.3.2 Outcomes? (e.g. International Classification of Diseases (ICD), Medical Dictionary for Regulatory Activities (MedDRA))				NA
9.3.3 Covariates and other characteristics?				NA
9.4 Is a linkage method between data sources described? (e.g. based on a unique identifier or other)				NA

Comments:

--

BOEHRINGER INGELHEIM Group of Companies

Non-interventional Study Protocol BI Study Number 0135-0350

Page 36 of 41
c36821715-01

Proprietary confidential information © 2021 Boehringer Ingelheim International GmbH or one or more of its affiliated companies

13. Section 10: Analysis plan	Yes	No	N/A	Section Number
10.1 Are the statistical methods and the reason for their choice described?				9.7
10.2 Is study size and/or statistical precision estimated?				9.5
10.3 Are descriptive analyses included?				9.7
10.4 Are stratified analyses included?				NA
10.5 Does the plan describe methods for analytic control of confounding?				9.7.1
10.6 Does the plan describe methods for analytic control of outcome misclassification?				NA
10.7 Does the plan describe methods for handling missing data?				NA
10.8 Are relevant sensitivity analyses described?				9.7.2

Comments:

14. Section 11: Data management and quality control	Yes	No	N/A	Section Number

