11.1 Does the protocol provide information on data storage? (e.g. software and IT environment, database maintenance and anti-fraud protection, archiving)				9.8
11.2 Are methods of quality assurance described?				9.10.1
11.3 Is there a system in place for independent review of study results?				NA

Comments:

15. Section 12: Limitations	Yes	No	N/A	Section Number
12.1 Does the protocol discuss the impact on the study results of:				
12.1.1 Selection bias?				9.9
12.1.2 Information bias?				9.9
12.1.3 Residual/unmeasured confounding? (e.g. anticipated direction and magnitude of such biases, validation sub-study, use of validation and external data, analytical methods).				NA

BOEHRINGER INGELHEIM Group of Companies**Non-interventional Study Protocol**
BI Study Number 0135-0350Page 37 of 41
c36821715-01

Proprietary confidential information © 2021 Boehringer Ingelheim International GmbH or one or more of its affiliated companies

15. Section 12: Limitations	Yes	No	N/A	Section Number
12.2 Does the protocol discuss study feasibility? (e.g. study size, anticipated exposure uptake, duration of follow-up in a cohort study, patient recruitment, precision of the estimates)				9.1 and 9.2

Comments:

16. Section 13: Ethical/data protection issues	Yes	No	N/A	Section Number
13.1 Have requirements of Ethics Committee/ Institutional Review Board been described?				10
13.2 Has any outcome of an ethical review procedure been addressed?				10
13.3 Have data protection requirements been described?				10

Comments:

17. Section 14: Amendments and deviations	Yes	No	N/A	Section Number

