7.3 STUDY POPULATION

No sampling will be undertaken and all patients who meet all the inclusion criteria and none of the exclusion criteria will be included.

The inclusion and exclusion criteria are listed below:

Inclusion criteria:

- Patients registered in the ZSQCC platform from Jan 2017 to Mar 2020
- ≥ 18 years of age
- Diagnosed with AIS at admission
- Arrived or admitted to the hospital within 4.5 hours of symptom onset
- If treated with IV rt-PA: received IV rt-PA within 4.5 hours of symptom onset

Exclusion criteria:

- Documented IVT contraindication except age to IV rt-PA treatment according to the SmPC
- Missing any one of the key data (age, gender, baseline National Institutes of Health Stroke Scale [NIHSS], time of symptom onset, time of hospital arrival or admission, IVT or not, time of IV rt-PA treatment)
- Received thrombolysis agents other than rt-PA (urokinase, tenecteplase, recombinant plasminogen activator, prourokinase, streptokinase)
- Received endovascular treatment
- Received IV rt-PA after 4.5 hours of symptom onset

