10.2 HANDLING OF MISSING VALUES

For comorbidities at baseline (including diabetes, coronary artery disease, atrial fibrillation, prior stroke/transient ischaemic attack, and hypertension) and co-medication at baseline (including anti-platelet, oral anticoagulation, and lipid lowering), missing values will be regarded as absence of those comorbidity and co-medication. For medical insurance status, smoking status, and hospital level, missing values will be assigned to a separate group. Medians will be imputed for missing values of Pre-stroke mRS.

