To account for potential confounding, the 2 cohorts will be 1:1 or 2:1 matched by baseline characteristics using the Propensity Score Matching method. The feasibility of PSM will be evaluated based on available sample size and descriptive results. If patient characteristics between the 2 cohorts are significantly different, i.e., less than 50% of patients in the IV rt PA cohort can be matched to the non-reperfusion cohort based on PSM, the study design will be re-evaluated before proceeding to analysis. The PSM aims to balance the 2 cohorts on baseline covariates. The propensity score model will include age, gender, baseline NIHSS/NIHSS categories (0-4, 5-10, 11-15, 16-21, and ≥ 22), pre-stroke mRS, medical insurance status, smoking status, hospital level, diabetes, coronary artery disease, atrial fibrillation, prior stroke/transient ischaemic attack, hypertension, anti-platelet, lipid lowering, oral anticoagulation, and time from symptom onset to hospital admission. The method of Nearest Neighbour matching will be used (a maximum caliper width equal to 0.2 of the standard deviation of the logit of the propensity score) to select the matched samples. Then we will compare the baseline characteristics of the 2 propensity-score-matched cohorts. The absolute standardized difference (ASD) between the 2 PS-matched cohorts will be calculated, where at least 0.1 ASD will be considered a significant difference. For baseline covariates that are not sufficiently balanced after PSM, they will be included in an appropriate multivariate model to adjust for those differences.

For the primary outcome, a comparison of the percentage of 1-year* all-cause mortality (mRS=6) between the 2 matched cohorts will be conducted using a Chi-square test. A Kaplan-Meier curve with log-rank test will be used to analyse the data. Cox regression models will be used to estimate hazard ratios (95% confidence interval) between the 2 matched cohorts.

For the secondary outcomes, descriptive summaries will be conducted in the PS-matched cohorts separately. For the categorical variables including functional independence (mRS 0-2), favourable clinical outcome (mRS 0-1), and mRS 5-6 at 1 year, the Chi-square test and conditional logistic regression model will be conducted. For the distribution of mRS score at 1 year, the Wilcoxon rank sum test and ordinal logistic regression model will be performed to calculate the odds ratio and 95% CI.

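### The propensity score omits onset year and captures centre only through hospital grade, and missing pre-stroke mRS is set to the median: an avoidable, unquantified risk of residual confounding in the primary hazard ratio

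*SAP*

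**What the plan says.** SAP 11.1 gives a closed list for the score: "The propensity score model will include age, gender, baseline NIHSS/NIHSS categories", followed by pre-stroke mRS, insurance, smoking, hospital level, five comorbidities, three co-medications and the interval from onset to admission. Hospital level (Grade 2 or 3) is the only centre-related term. The interval is the only time term, and it is not calendar time. Neither centre nor onset year is a covariate in SAP 8.3 or in Protocol 9 C).

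SAP 7.2 states 80 centres and January 2017 to March 2020. The limitations in Protocol 9 I) include "The treatment adapted for AIS patients may be different among stroke centres" and "The completeness of the captured data and potential for misclassification of data could differ among stroke centres", and concede that unmeasured confounding cannot be ruled out.

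SAP 7.3 excludes patients with "Missing any one of the key data (age, gender, baseline National Institutes of Health Stroke Scale [NIHSS], time of symptom onset" and further items. Onset time is therefore known for every analysed patient. Pre-stroke mRS is not on that list, so patients without it stay in. For them SAP 10.2 says "Medians will be imputed for missing values of Pre-stroke mRS", while missing smoking, insurance and hospital level go to a separate group.

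Under SAP 11.1, baseline covariates with an absolute standardised difference (ASD) of 0.1 or more after matching are adjusted for in a multivariate model. Neither document describes a sensitivity analysis.

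**The concern.** A matched comparison removes confounding only by what is in the score. If centres or years with more rt-PA use also had lower (or higher) mortality for other reasons, part of that difference would be read as an rt-PA effect on death. Two hospital grades cannot represent 80 centres. The 0.1 rule offers no protection here, because centre and year are not listed covariates and so no ASD is planned for them.

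Pre-stroke mRS raises a different problem. Every missing value becomes the same number. If the ASD is computed on those filled-in values, which the SAP leaves open, true imbalance among patients with missing data is invisible and the adjustment rule does not fire.

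**Working it through.** **Planned effect.** The SAP plans for HR 0.79, two-sided alpha 0.05 and 90% power. By Schoenfeld's formula, events = (1.960 + 1.282)² / [p(1−p)(ln 0.79)²]. This gives 757 at 1:1 (SAP: 756) and 851 at 2:1 (SAP: 855), so the stated figures reproduce. The effect at stake is |ln 0.79| = 0.236 on the log scale.

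**Matching ratio.** With about 8,500 rt-PA patients and 3,200 controls, 1:1 matching can use at most 3,200/8,500 = 38% of rt-PA patients, below the SAP's 50% threshold. A 2:1 ratio can reach 6,400/8,500 = 75%. The illustrations therefore use 2:1.

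**Inputs.** The documents give no between-centre variation, time trend or share of missing mRS. Those inputs are assumed. The simulations use 11,700 patients, 1-year mortality of 14%, a caliper of 0.2 SD of the logit, and complete 2:1 sets. The true HR is 1 for centre and year; the mRS results are relative to complete data.

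**Centre.** There are 80 unequal centres, with hospital grade in the score and 600 runs per scenario. Centre SDs are 0.5 to 1.0 on the treatment logit and 0.2 to 0.3 on the log hazard; r is the correlation between the two.

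| r | HR, smaller / larger SDs | Two-sided rejection |
|---|---|---|
| 0 | 1.000 / 1.000 | 4.7% / 6.0% |
| −0.3 | 0.983 / 0.949 | 6.0% / 15.5% |
| −0.5 | 0.969 / 0.915 | 7.8% / 28.7% |
| +0.3 | 1.026 / 1.055 | 4.8% / 13.7% |
| +0.5 | 1.036 / 1.097 | 8.7% / 29.5% |

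The Monte Carlo SE is 0.003. A centre-stratified Cox model in the same matched patients gave HR 1.00 to 1.01 and 3.2% to 5.2% rejection, with an SE 3% to 8% wider.

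A separate simulation (70 runs per scenario) agreed at r = −0.5 with the larger SDs: HR 0.91 to 0.92. It also showed a limit of stratification alone. With strong measured confounding the stratified HR was 0.95 even at r = 0, because matching that ignores centre can leave measured covariates unbalanced within centres. Adding the score covariates to the stratified model restored 0.99 to 1.01.

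**Onset year** (300 runs). Assumed trends were +10% to +60% a year in rt-PA odds, together with −3% to −10% a year in hazard. Without year in the score the HRs were 1.004, 0.990 and 0.962, and the ASD for year was 0.09 to 0.42. With year in the score they were 1.004, 1.004 and 0.996. A trend in only one of treatment and mortality gave 1.00.

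**Pre-stroke mRS, closed form.** Take the median as no disability. Let p1 and p0 be the shares with hidden disability in the rt-PA and control cohorts, and g its mortality ratio. Bias factor = [p1(g−1)+1] / [p0(g−1)+1].

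- 10% missing in both, disabled 10% vs 20% of the missing, g = 2: 1.01/1.02 = 0.99.
- 5% vs 20% missing, same disability, g = 3: 1.01/1.08 = 0.935.
- 10% vs 30% missing, disabled 10% vs 30%, g = 3: 1.02/1.18 = 0.864, an extreme case.

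**Pre-stroke mRS, simulated** (200 runs; disability 15% to 25% with HR 2.0 to 2.5).

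- Missing in 20% to 30% of controls against 10% of rt-PA patients: HR 0.974 to 0.926 relative to complete data. The ASD was 0.01 on imputed values but 0.07 to 0.15 on true values.
- Equal 10% missing: 0.992. Reversed (10% of controls, 30% of rt-PA patients): 1.027.
- With a missing category: 0.987 to 1.001. With multiple imputation: 0.996 to 1.002.

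A missing category would expose the difference. For 20% vs 10% missing, the ASD of the missing share is 0.10/√((0.16+0.09)/2) = 0.28; for 30% vs 10% it is 0.20/√((0.21+0.09)/2) = 0.52.

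**Scale.** The largest centre shifts are |ln 0.915| = 0.089 and ln 1.097 = 0.093, or 38% and 39% of 0.236. The smaller-SD centre scenarios with r other than 0 shift the HR by about 7% to 15% of it.

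**The case against.** The strongest reply is that every biasing input above is assumed. The largest shifts come from the most extreme centre scenarios, and both directions are equally arguable. That stands. A reader might infer that the planned HR is biased in favour of rt-PA, or take 38% as an expected bias; the documents support neither.

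Hospital level gives some control for centre, so it would be wrong to say that the plan ignores centre altogether. It is, however, only two grades for 80 centres, and the simulated shifts arose with it in the score. SAP 9 promises centre characteristics but does not confirm a centre identifier in the analysis file, so a centre analysis has to be conditional.

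Onset year is the weakest of the three. Only steep trends in both treatment and mortality move the HR noticeably, and the documents state no trend in either. If only treatment has a trend, adding year costs matches and removes no bias. The argument for adding it is that onset time is already mandatory and the cost in matches is usually small.

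For pre-stroke mRS, the effect is small if few values are missing or if missingness is similar in the two cohorts. That the imbalance would be hidden depends on how the ASD is computed.

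Finally, Protocol Annex 2 answers Yes to "10.8 Are relevant sensitivity analyses described" and cites 9.7.2, but both the contents list and the text of Protocol 9 G) go from the main analysis (i) to "iii. Safety analysis". Annex 2 also marks "12.1.3 Residual/unmeasured confounding" not applicable, although Protocol 9 I) raises it. A reader might take the dangling reference as a sign of bias or of a withdrawn analysis. The documents show only a reference with no target, which is a clerical matter.

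**Conclusion.** The concern holds as an avoidable risk, not a demonstrated bias. Three facts are certain from the text: centre enters the score only through hospital grade, onset year does not enter at all, and missing pre-stroke mRS becomes the median. No planned analysis would reveal whether any of these matters. Size and direction depend on between-centre variation, time trends and missing shares that the documents do not give, and the effect may be nil. Under the assumed ranges the simulated shifts run from none to just under two fifths of the planned log hazard ratio. This justifies inexpensive changes made before the analysis; it is not a reason to reject the design.

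**What to change.** **1. Onset year (SAP 8.3 and 11.1).** Add calendar year of onset (2017 to 2020), derived from onset time, to the covariates, the score and the ASD table. State that if this or change 2 takes matching below 50% of rt-PA patients, the existing re-evaluation rule applies. Report the HR without the added term as well.

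**2. Pre-stroke mRS (SAP 10.2).** Report missingness by cohort before and after matching. Replace the median with the separate missing category already used for smoking and insurance, and include that category in the ASD. Add multiple imputation as a sensitivity analysis: impute, refit the score, match and fit the Cox model in each data set, then pool the log HRs by Rubin's rules.

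**3. Centre (SAP 11.1).** If a centre identifier is in the analysis file, prespecify as a sensitivity analysis of the primary HR a Cox model in the matched cohorts, stratified by centre and adjusted for the score covariates. Report how many centres have only one cohort. If there is no identifier, state that as a limitation.

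**4. Checklist (Protocol Annex 2).** Correct the 10.8 reference to 9.7.2.

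**Cost.** The changes need extra programming but no new data for 1 and 2. Centre stratification widened the SE by 3% to 8% in the simulation; one-cohort centres held on average at most 0.2% of matched patients (2.2% in the worst run). Changes 1 and 2 together cut rt-PA patients in complete 2:1 sets from about 62% to 55–57% with moderate assumed trends and 20% vs 10% missing (7,061 to 7,280 patients in all). In the two most extreme mixes the share fell to 49.5% and 47% (6,306 and 6,047 patients, against 6,069 planned), or 58–60% if controls with only one match are kept. A missing category does not remove all bias, hence the multiple-imputation check.

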7. RESEARCH METHODS

7.1 STUDY DESIGN

This study is a non-interventional study (NIS) based on existing data. We will analyse data of AIS patients aged ≥ 18 years in China collected from the ZSQCC platform. [\[P21-04780\]](#), [\[P21-04783\]](#), [\[P21-04784\]](#), [\[P21-04779\]](#), [\[P21-04782\]](#)

Approximately 11700 AIS patients in total are recorded in the ZSQCC platform and will be analysed in this study. There were approximately 8500 AIS patients (≥ 18 years of age) who were treated with IV rt PA and 3200 patients who were admitted to the hospital within 4.5 hours of symptom onset and did not receive reperfusion treatment from Jan 2017 to Mar 2020. In the China National Stroke Registry I (2007-2008), the 12-month mortality rate for post-stroke patients was approximately 14%. [\[R21-1852\]](#) For this study, it is assumed that 1-year mortality is 12% and 15% for the rt-PA treatment cohort and the cohort who did not receive reperfusion, respectively. In total, 6069 patients with a treatment ratio 2:1 are needed to observe 855 events and to detect the difference (hazard ratio=0.79) with a 2-sided alpha of 0.05 and 90% power. In addition, considering a treatment ratio 1:1 with the same assumption described above with power of 90% at a 2-sided, 5% significant level, roughly 5400 patients are needed to observe 756 events to detect the difference.

[figure not shown]
Patients meeting the inclusion and exclusion criteria will be divided into 2 cohorts:

- IV rt-PA cohort: Patients who received IV rt-PA within 4.5 hours of symptom onset
- Non-reperfusion cohort: Patients who arrived or were admitted to the hospital within 4.5 hours of symptom onset and did not receive any reperfusion treatment

Propensity score matching (PSM) will be used to match the baseline characteristics between the above 2 cohorts. The primary, secondary outcomes, as well as baseline characteristics will be compared between the matched cohorts.

The flow of data selection for each of the 2 reporting patient cohorts is depicted in Figure 1 below.

Figure 1 Patient cohorts selected for the non-interventional study

Note: dotted lines: excluded

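### A 0.1 standardised-difference check on baseline NIHSS can pass while the severity distribution still differs between the matched cohorts, and nothing then adjusts for it

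*SAP*

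**What the plan says.** SAP section 11.1 lists the propensity-score covariates and gives severity as "baseline NIHSS/NIHSS categories (0-4, 5-10, 11-15, 16-21, and ≥ 22" (the category list closes there). It does not choose between the score and the five categories, so one linear NIHSS term is permitted. Matching is nearest neighbour, 1:1 or 2:1, with a caliper of 0.2 SD of the logit of the propensity score.

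Balance after matching has one criterion: "The absolute standardized difference (ASD) between the 2 PS-matched cohorts will be calculated, where at least 0.1 ASD will be considered a significant difference". The protocol's main analysis (section 9, part G) has the same threshold: "an ASD of at least 10% ASD will be considered a meaningful difference". Neither document gives a formula for the standardised difference (ASD), says whether NIHSS is assessed as a score or by category, or names a variance ratio or other distributional criterion. A covariate goes into the outcome model only if it is insufficiently balanced after matching.

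Other parts of the plan touch on severity without acting on it. SAP 11.1 tabulates SD, median, IQR and range, allows continuous variables to be grouped when needed, and analyses outcomes in five NIHSS strata. The protocol uses reasons for non-treatment descriptively only.

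**The concern.** Baseline NIHSS is the plan's only measure of stroke severity. For a continuous score, the ASD is conventionally the difference in means over a pooled SD, so it cannot see two cohorts with the same mean and different spread.

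If very mild and very severe patients are both treated less often, a linear NIHSS term has a slope near zero. The propensity score is then driven by the other 15 covariates on the SAP's list, and matching does little to NIHSS. The matched means agree, the check passes, and the adjustment rule is not triggered, although controls hold more patients at both extremes. Part of any mortality difference would then be residual confounding in a covariate reported as balanced.

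**Working it through.** **1. The plan's own figures.** Inputs from SAP 7.1: "2-sided alpha of 0.05 and 90% power"; "it is assumed that 1-year mortality is 12% and 15% for the rt-PA treatment cohort and the cohort who did not receive reperfusion"; "6069 patients with a treatment ratio 2:1 are needed to observe 855 events and to detect the difference (hazard ratio=0.79"; and, for 1:1, "roughly 5400 patients are needed to observe 756 events to detect the difference". Schoenfeld: events = (1.960 + 1.282)² / (p(1−p)(ln HR)²) = 10.507 / (p(1−p) × 0.05557).
- 1:1, p(1−p) = 1/4: 756.4 (stated 756).
- 2:1, p(1−p) = 2/9: 851.0 (stated 855).

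These reproduce closely and are not disputed. The planned log hazard ratio, ln 0.79 = −0.236, is the yardstick below.

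**2. A mean-based ASD can pass despite poor balance.** Assumed shares in the five NIHSS categories, with assumed representative values 2, 7, 13, 18 and 25:

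| | 0-4 | 5-10 | 11-15 | 16-21 | ≥22 | Mean | Mean of squares | Variance |
|---|---|---|---|---|---|---|---|---|
| rt-PA | 25% | 45% | 18% | 9% | 3% | 8.36 | 101.38 | 31.49 |
| Control | 45% | 20% | 12% | 15% | 8% | 8.56 | 130.48 | 57.21 |

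- ASD of the score = 0.20 / √((31.49 + 57.21)/2) = 0.20 / 6.66 = 0.03: passes.
- ASD of the 5-10 category = 0.25 / √((0.45×0.55 + 0.20×0.80)/2) = 0.55: fails. The other four are 0.43, 0.17, 0.19 and 0.22: all fail.
- Variance ratio, rt-PA/control = 31.49/57.21 = 0.55.

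**3. The sign depends on the mortality curve.** With the same shares and no treatment effect, the ratio of average risk or starting hazard (rt-PA/control) is:
- log-hazard rising 0.06 per point: 1.759/1.874 = 0.94; 0.12 per point: 3.600/4.514 = 0.80;
- risk proportional to NIHSS: 8.36/8.56 = 0.98;
- risk proportional to √NIHSS (concave): 2.725/2.635 = 1.03.

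This imbalance is larger than any in step 4, so it shows the mechanism and not the expected size.

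**4. Simulated matching.** Cohort sizes come from SAP 7.1 (about 8500 rt-PA, and "3200 patients who were admitted to the hospital within 4.5 hours of symptom onset and did not receive reperfusion treatment"). Matching was 1:1 with a 0.2 SD caliper, true HR 1, and NIHSS linear in the propensity score. Other covariates were in the score except in the last row. The NIHSS distribution, selection and mortality are assumptions. Graded selection lowers the treatment log-odds by the stated amount at NIHSS 0-4 and by the same amount per 7 points above 15. Step selection lowers it by the three stated amounts at 0-4, 16-21 and ≥22. In the graded two-ended runs the log-hazard rises with NIHSS, for example by 0.06 to 0.12 per point. The step rows span logistic, category-based and linear mortality.

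| Selection | Score ASD | Variance ratio (rt-PA/control) | Largest category ASD | Apparent HR |
|---|---|---|---|---|
| Graded 0.4 | 0.01 | 0.72-0.73 | 0.16 | 0.94-0.98 |
| Graded 0.7 | 0.01 | 0.58-0.59 | 0.27-0.28 | 0.91-0.97 |
| Graded 1.0 | 0.01 | 0.49-0.50 | 0.39 | 0.88-0.95 |
| Two-ended, further runs | 0.01-0.02 | 0.48-0.72 | 0.17-0.41 | 0.84-0.97 |
| Step 1.2/1.2/1.8 | 0.02 | 1/1.63 = 0.61 | 0.44 | 0.93-1.01 |
| Step 0.7/0.8/1.2 | 0.02 | not reported | 0.28 | 0.98-1.02 |
| Step 1.5/0.8/1.2 (more at mild end) | 0.06 | 1/1.19 = 0.84 | 0.40 | 1.02-1.05 |
| Mild end 1.5, severe end 0.7 | 0.04 | not reported | not reported | 1.02-1.07 |
| Two-ended, NIHSS the only covariate | not reported | about 1.00 | 0 | 0.999-1.000 |

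Every score ASD shown passes the 0.1 rule. With only mild strokes withheld, HR was 0.99.

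**5. Alternatives under two-ended graded selection.**
- Piecewise-linear NIHSS (a simple spline): HR 0.97-1.02, with about 1% to 4% fewer pairs.
- Five categories alone: category ASDs about 0.02, variance ratio 0.80-0.92, yet HR 0.92-0.99, because severity still varies within wide categories such as ≥22. Categories gave 1.00 only where the simulated selection was itself constant within categories.

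**The case against.** A reader might infer that the SAP judges NIHSS by its mean alone, so that adjustment can never be triggered. The text does not say that. It gives no ASD formula and names the five categories in the same paragraph. If balance is tabulated by category, values of 0.16 to 0.44 fail the 0.1 rule and the existing adjustment applies. This stands: the gap is that the plan does not require the check that would work.

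A reader might also infer that the hazard ratio is biased toward rt-PA. That needs two-ended withholding in roughly balanced proportion and mortality convex in NIHSS, and the documents establish neither. Heavier withholding at the mild end turns the bias against rt-PA. Excluding documented contraindications (other than age) and endovascular treatment may also change who remains untreated.

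The mechanism needs other covariates that drive treatment. With NIHSS alone, a linear score is a monotone function of NIHSS, matching acts on NIHSS itself, and no bias appears. The SAP's model does contain other covariates, but the size depends on their strength, which is unknown.

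The planned tables could reveal the problem, since a variance ratio of 0.5 to 0.7 would show in the SDs. No rule acts on them, however. The NIHSS strata offer little protection. The protocol runs subgroups only where each reaches 5400 (1:1) or 6069 (2:1) patients, whereas 1:1 matching of 3200 controls yields at most 6400 patients in all. The SAP omits that condition, but stratum results would not correct the primary hazard ratio.

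**Conclusion.** The gap is real, and its consequence is conditional. The SAP permits a linear NIHSS term, has one balance threshold, and adjusts only for covariates that fail it. If NIHSS is checked as a score, the rule can pass a materially different severity distribution.

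Under two-ended withholding and convex mortality, the apparent hazard ratio was about 0.84 to 0.98 with no treatment effect. On the log scale that is ln 0.98/ln 0.79 = 9% to ln 0.84/ln 0.79 = 74% of the planned effect. Under other selection patterns or mortality curves the bias was near zero or reversed, up to 1.07. Neither the sign nor the size can be settled from the documents, so this does not show that the study's result will favour rt-PA.

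It is also tempting to conclude that a stricter balance rule would be enough. It would not: category ASDs below 0.1 with a variance ratio of 0.8 to 1.25 would pass the categories-only model, which still gave about 0.94 to 0.98 in runs that met those limits.

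**What to change.** Amend SAP 11.1 before outcomes are examined:
- Enter NIHSS in the propensity score as a spline with prespecified knots, replacing the open choice between score and categories.
- Include NIHSS, as a spline, in the Cox and logistic outcome models whether or not the balance check fails.
- Report the ASD in each of the five NIHSS categories and the NIHSS variance ratio, before and after matching, as diagnostics and not as the trigger for adjustment.

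The spline in the propensity score is not sufficient in every case: with much heavier withholding at the mild end (1.5 against 0.7), a piecewise-linear term still left HR 0.93 to 0.98. That is why outcome-model adjustment should be unconditional. The simulations above did not test that second step.

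The cost is about 1% to 4% fewer matched pairs, a few more table columns and short SAP wording. All the data are already required, since missing NIHSS is an exclusion. The adjusted hazard ratio is conditional on NIHSS, so the report should say so and show the unadjusted matched estimate beside it.
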